2.10.2.2. Plasma Concentration Analysis

Pre-dose and single post-dose plasma concentrations of VK5211 at Visits 2, 3 and 4 and the single plasma concentration at Visit 5 will be summarized using mean, geometric mean, standard deviation, coefficient of variation (CV%), median, minimum and maximum.

2.10.3. Exploratory Objectives

2.10.3.1. Physical Performance Assessments

2.10.3.1.1. 6 Minute Walk Test and BORG Scale

The 6MWT total distance walked will be analyzed using an Analysis of Covariance model with the baseline value as a covariate with treatment and region (country) as factors. Observed values and change from baseline will be summarized using mean, standard deviation, coefficient of variation (CV%), median, minimum and maximum. The number and percent of subjects that walked more than 150, 200, 250 and 300 meters and who had a change from baseline of more than 50, 100 and 150 meters will be presented.

The Borg Scale is a categorical scale with 12 possible values. There are sufficient number of categories that the Borg Scale will be analyzed as a continuous variable. The Borg Scale will be analyzed using an Analysis of Covariance model with the baseline value as a covariate with treatment and region (country) as factors. Observed values and change from baseline will be summarized using mean, standard deviation, coefficient of variation (CV%), median, minimum and maximum.

2.10.3.1.2. Grip Strength

Grip strength will be analyzed using a Repeated Measures Analysis of Covariance model with average baseline assessment as a covariate, treatment and region (country) as factors and measurement as the repeated measure (since 2 measures are being taken). Observed average, change from baseline average and placebo adjusted average change from baseline will be summarized using mean, standard deviation, coefficient of variation (CV%), median, minimum and maximum.

2.10.3.1.3. Short Physical Performance Battery

SPPB individual scores and total scores will be summarized using frequency counts and summary statistics. Observed values and change from baseline will be summarized.

Number and percent of subjects that:

- Improved by at least 1, 2 and 3 points,
- Whose total score is greater than 7, and
- Whose 4-meter gait speed increased by more than 0.1 m/sec

will be presented.

A Cochran-Mantel-Haenszel row mean score will be used to test for differences in frequency counts between treatment groups. An Analysis of Covariance with base value as a covariate and country as factor will be used to test for differences in the mean.

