9.3.2 Physical Performance Assessments

The 6MWT total distance walked will be analyzed using an Analysis of Covariance model with baseline value as a covariate and treatment as a primary factor. Observed values, change from baseline and placebo adjusted change from baseline will be summarized using mean, standard deviation, coefficient of variation (CV%), median, minimum and maximum.

Grip strength will be analyzed using an Analysis of Covariance model with baseline value as a covariate and treatment as a primary factor. Observed values, change from baseline and placebo adjusted change from baseline will be summarized using mean, standard deviation, coefficient of variation (CV%), median, minimum and maximum.

SPPB score will be summarized using frequency counts. Observed values and change from baseline will be summarized. A Kruskal-Wallis test (ANOVA on ranks) will be used to test for differences between treatment groups.

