1.3.3. Exploratory Objectives

The exploratory objectives of this study are to determine the efficacy of VK5211 compared to placebo after 12 weeks of treatment by:

- Physical Performance Assessments
 - 6 Minute Walk Test (6MWT) and BORG Scale
 - Grip Strength
 - Short Physical Performance Battery (SPPB)
- Patient Reported Outcomes
 - Pre- and Post-fracture Physical and Instrumental Activities of Daily Living (PADLs/IADLs)
 - Short Form-36 (SF-36)

2. Detailed Statistical Methods

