2.10.3.2.2. Short Form-36

The SF-36 individual subscales (Physical Functioning (PF), Role-Physical (RP), Bodily Pain (BP), General Health (GH), Vitality (VT), Social Functioning (SF), Role-Emotional (RE) and Mental Health (MH)) , component measures (Physical Health Component Score and Mental Health Component Score) and total score (Physical Health Component Score + Mental Health Component Score) will be analyzed using an Analysis of Covariance model with baseline value as a covariate and treatment and region (country) as factors. Observed values, and change from baseline will be summarized using mean, standard deviation, median, minimum and maximum.

Derivation of the SF-36 subscales are defined in section 2.15.

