2.13. Analysis of Subgroups

There are no subgroup analyses planned for this study, but there is a plan to perform analyses to test for significant factor effects.

At the 3 month and 6 month analyses, we will test for a significant sex effect. Sex will be added as a factor into the ANCOVA models with least squares means and 95% confidence intervals being presented by treatment and sex. P-Values will be presented for the sex effect, treatment effect and sex*treatment interaction.

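### The SPPB analysis of covariance omits treatment, so as written it gives no VK5211-placebo comparison and conflicts with SAP 2.13

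*SAP*

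**What the plan says.** SAP 2.10.3.1.3 plans two tests for SPPB. The first is explicitly between arms: "A Cochran-Mantel-Haenszel row mean score will be used to test for differences in frequency counts between treatment groups". The second is the ANCOVA: "An Analysis of Covariance with base value as a covariate and country as factor will be used to test for differences in the mean". The second sentence names one covariate and one factor. It does not mention treatment, and it does not say between which groups the means are compared.

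The neighbouring SAP sections are worded differently:
- Six-minute walk and Borg (2.10.3.1.1): "with the baseline value as a covariate with treatment and region (country) as factors".
- Grip strength (2.10.3.1.2): "average baseline assessment as a covariate, treatment and region (country) as factors".
- SF-36 (2.10.3.2.2): "baseline value as a covariate and treatment and region (country) as factors".

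The primary endpoint (2.10.1) and the other DXA measures and bone turnover markers (2.10.2.1) also name treatment and region (country).

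SAP 2.13 adds sex to the ANCOVA models and then says: "P-Values will be presented for the sex effect, treatment effect and sex*treatment interaction". Tables 14.2.09.1.2 and 14.2.09.2.2 are the SPPB sex-effect tables. SAP 2.11 lists SPPB among the variables in the Month 3 primary analysis.

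Protocol 9.3.2 has no ANCOVA for SPPB. Its test is: "A Kruskal-Wallis test (ANOVA on ranks) will be used to test for differences between treatment groups".

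**The concern.** SAP 1.3.3 sets the purpose of this analysis: "The exploratory objectives of this study are to determine the efficacy of VK5211 compared to placebo after 12 weeks of treatment by" a list of measures that includes SPPB. A model holding only baseline and country does not serve that purpose, because its only factor test is for country.

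The sentence is the operative model statement, the one a programmer implements and an auditor checks, and the protocol has no SPPB ANCOVA to fall back on. If the programmer follows it, the ANCOVA output says nothing about VK5211. If the programmer adds treatment without a change to the SAP, the reported analysis differs from the written plan. SPPB is one of seven variables read out by treatment group at Month 3, so the question arises at the first unblinded summary and not only in the final report.

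**Working it through.** The plan states no power, sample size or alpha for SPPB, so there is no figure to reproduce. The check compares model terms across sections and then counts degrees of freedom.

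**1. Terms named in each SAP efficacy ANCOVA**

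| Endpoint | SAP section | Baseline | Treatment | Country |
|---|---|---|---|---|
| TBLH lean mass (primary) | 2.10.1 | yes | yes | yes |
| Other DXA measures, bone turnover markers | 2.10.2.1 | yes | yes | yes |
| Six-minute walk, Borg | 2.10.3.1.1 | yes | yes | yes |
| Grip strength (repeated measures) | 2.10.3.1.2 | yes | yes | yes |
| SPPB | 2.10.3.1.3 | yes | **no** | yes |
| SF-36 | 2.10.3.2.2 | yes | yes | yes |

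SPPB is the only exception.

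**2. Degrees of freedom**

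Inputs: four arms (SAP 1.2) and about 92 completers, roughly 23 per arm (SAP 2.14). The documents do not give the number of countries; three is assumed for illustration only.

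- As written: intercept 1 + baseline 1 + country (3 − 1) = 4 parameters. Residual df = 92 − 4 = 88. Treatment df = 0, so there is no VK5211-placebo estimate, interval or p-value.
- With treatment added: 4 + (4 − 1) = 7 parameters. Residual df = 92 − 7 = 85. Treatment df = 3, which gives an overall test and three contrasts with placebo.

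Fitting both models to simulated data of this shape confirmed these counts: 88 and 85 residual df, with treatment parameters only in the second model. The treatment df (0 against 3) does not depend on the assumed number of countries.

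**3. Consistency with SAP 2.13**

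That section adds sex, and only sex, to the ANCOVA models. It then promises least squares means by treatment and sex, with p-values for sex, treatment and their interaction.

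- If the base SPPB model is baseline + country, adding sex gives baseline + country + sex, which has no treatment effect or interaction to report.
- The promised output is possible only if treatment is already in the base model.

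SPPB sex-effect tables are planned for both the ITT and the Per Protocol populations, so 2.10.3.1.3 and 2.13 cannot both be followed literally for this endpoint.

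**The case against.** The strongest reply is that the intent is obvious. The preceding sentence in 2.10.3.1.3 compares treatment groups, and the ANCOVA sentence reads as its companion with the groups left implicit. SAP 1.3.3 asks for a comparison with placebo, and 2.13 presupposes a treatment term. The table shells, which might settle the matter, are in a separate file. All of this stands and makes a drafting omission the likely explanation. It makes the correction uncontroversial; it does not remove the conflict between the two sections.

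A reader might infer more than the documents support:

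- **That SPPB has no treatment test.** It has one, the CMH row mean score between treatment groups, and the planned sex-effect model is also meant to report a treatment effect.
- **That a protocol comparison was lost.** The protocol's Kruskal-Wallis test is not baseline-adjusted either. The SAP keeps a between-treatment test with no stated baseline adjustment and adds an ANCOVA.
- **That the loss equals a given share of the subjects.** If the CMH test were applied to follow-up scores, the approximate variance ratio against ANCOVA would be 1/(1 − r²), where r is the baseline to follow-up correlation: 1.33 at r = 0.5 and 2.78 at r = 0.8. On change scores it would be 2/(1 + r): 1.33 and 1.11. The SAP does not say which variable is tested and gives no r. Both formulas describe comparisons of means, not a CMH test on an ordinal score. No single figure is defensible.
- **That multiple imputation would have nothing to pool.** Arm means could still be pooled. Only the treatment contrast from this ANCOVA would be missing.
- **That a key endpoint is compromised.** Both documents class SPPB as exploratory, and the primary endpoint's model names treatment.

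**Conclusion.** The point holds in a limited form. The SPPB ANCOVA is wrong as written: it has 0 treatment degrees of freedom where 3 are needed, it is the only efficacy ANCOVA in the SAP without treatment, and it contradicts 2.13. Read literally, the plan lacks the main baseline-adjusted comparison of VK5211 with placebo for SPPB.

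The consequence is small. The endpoint is exploratory, a between-treatment test remains, and the context points to a drafting omission rather than a deliberate choice. The conclusion rests on the text and the number of arms, and needs no assumption about correlations, effect sizes or the number of countries. It deserves correction because SPPB is part of the Month 3 readout, where the model used should match the model written.

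**What to change.** In SAP 2.10.3.1.3, replace the ANCOVA sentence with one that specifies an Analysis of Covariance with "baseline value as a covariate and treatment and region (country) as factors", used to compare mean SPPB between treatment groups. This matches the SF-36 section and makes the sex-effect model in 2.13 follow directly.

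The cost is one phrase. Data collection, sample size and trial conduct do not change. The correction should be dated before treatment-level results are produced for the Month 3 primary analysis; if that has passed, the study report should state that treatment was included and why.

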2.10.3.2. Patient Reported Outcomes

2.10.3.2.1. Pre- and Post-Fracture Physical and Instrumental Activities of Daily Living

For the analysis of the PADLs/IADLs, entirely dependent means that the subject is unable to perform the activities without assistance. For Example:

- The IADL Q1 discusses how the subject got to places out of walking distance.
 - Responses that would not be entirely dependent are:
 - Response 1 (Travel alone on buses, taxis, or drive your own car)
 - Response 3 or 4 (Did not perform), if Q1a has a response of 1 (Independently)
 - Responses that would be entirely dependent are:
 - Response 2 (Have someone to help you or go with you when travelling)
 - Response 3 or 4 (Did not perform), if Q1a has a response of 2 (With Assistance) or 3 (Would not be able to at all).

A significant change from screening would be a change in the subjects entirely dependent rating. A significant positive change would be if someone was entirely dependent at screening, but independent at the post-baseline visit. A significant negative change would be if someone was independent at screening, but entirely dependent at the post-baseline visit.

The PADLs/IADLs will be analyzed as follows:

- Change in number of subjects entirely dependent in performing each activity of daily living from screening at each post-screening visit will be analyzed using the Cochran-Mantel-Haenszel Test.
- Difference in number of subjects entirely dependent in performing each activity of daily living at each visit between treatment groups will be compared using the Cochran-Mantel-Haenszel Test.
- Each activity of daily living for each visit collected will be summarized using mean, standard deviation, median, minimum and maximum.
- Significant change from screening for each activity of daily living will be analyzed using the Wilcoxon signed-rank test.

- Differences between treatment groups for each activity of daily living will be analyzed using the Kruskal-Wallis test on the change from screening value.

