4=Did not perform: non-health Reason

Go to Q4a

Q4a. If you did not house clean, could you clean:

1=Independently

2=With Assistance

3=Would not be able to at all

15.7 **Self-Reported Physical and Instrumental Activities of Daily Living**

POST-FRACTURE

INTRODUCTION

Thank you for participating in our study. I am going to be asking you questions that are written down for me in this booklet. For some of the questions, I will read you a list of response choices. For these questions, listen to the choices as I read them then choose the one that is closest to your situation. For other questions, I will not read a list, but I will ask you for either a yes or no, a number, or an answer of your own. I will let you know what kind of response I'd like as we are going along. Do you have any questions before we begin?

The intent of these questions is to ascertain whether the device connotes an increase in dependence. These items measure whether the participant required assistance to perform each of the activities listed below. Treat each item as one entity; if the participant needed help for **any** part of the item (e.g., *needs* help getting in bed but *does not need* help to get out of bed), code as Assistance Used.

When asking the question, emphasize **on average** and that we are referring to any period of time within the specified time frame.

We want to know if they used some device or equipment or the help of another person to do the activity. It is particularly important that the participant keep in mind our broad definition of "equipment assistance".

As incorporated in the instructions, the following examples are provided to the participant: using a walker, cane, or furniture for walking; using dressing sticks or shoe horns to get dressed; using raised toilet seats, bathseats, and grab bars in the toilet or tub; and using long-handled reachers. Please make sure that the participant keeps these examples in mind as s/he responds. Additional types of equipment include a seat raiser, blocks under chair legs, button hooks, and adaptive clothing. Decisions about whether other items constitute equipment will be more difficult to make.

If a response seems in opposition to a response provided elsewhere (e.g., reports using no help to get on and off the toilet, but previously reported using grab bars for the toilet seat), **clarify and correct the discrepancy with the participant.**

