If the participant has not performed an activity, determine if it was not performed due to health reasons or non-health reasons. You may need to ask whether s/he found it too difficult or unsafe to perform the activity (Did Not Perform: Health), or whether s/he did not have the opportunity or preferred not to do the activity (Did Not Perform: Non-health).

Post-Fracture Physical Activities of Daily Living (PADLs)

[all 16 items]

In this group of questions, I am interested in whether you had help in performing each of these activities.

By "help" I mean whether you used some device or equipment or the help of another person, to do the activity. Let me first give you some examples of what I mean when I ask whether you used equipment.

- To get dressed, some people use special dressing sticks or shoe horns.
- In the bathroom, raised toilet seats, bath seats, and grab bars in the toilet or tub are sometimes used.
- To reach things, you might use long-handled reachers.

Basically, I am interested in whether "in the past week" you used any devices or help from another person to perform these activities.

In the PAST WEEK, ON AVERAGE, did you use help to....

	No Help 0	Used Equip 1	Used Human Assist 2	Used Equip & Human Assist 3	Didn't perform: Health 4	Didn't perform: Non-health 5	Don't Know 7	Refused 8
q. Walk 10 feet or across a room								
If 1 or 3 selected indicate type of equipment 1=Cane(s)  2=Walker  3=Wheelchair  4=Crutches  5=Other 								
r. Walk one block on a level sidewalk								
If 1 or 3 selected indicate type of equipment 1=Cane(s)  2=Walker  3=Wheelchair  4=Crutches  5=Other 								
s. Climb 5 stairs								
t. Get into car								
u. Get in and out of bed								
v. Rise from an armless chair								
w. Put on a shirt/blouse								

x. Button a shirt/blouse								
y. Put on pants								
z. Put on socks, shoes on both feet								
aa. Get in/out of bath or shower								
bb. Wash all parts of body								
cc. Get on/off the toilet								
dd. Feed yourself after food is readied								
ee. Groom yourself (brush hair and teeth)								
ff. Reach for an item on the ground from sitting position								

Post-Fracture Lower Extremity Physical Activities of Daily Living (LPADLs)

[only 12 items]

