In this group of questions, I am interested in whether you had help in performing each of these activities.

By "help" I mean whether you used some device or equipment or the help of another person, to do the activity. Let me first give you some examples of what I mean when I ask whether you used equipment.

- To get dressed, some people use special dressing sticks or shoe horns.
- In the bathroom, raised toilet seats, bath seats, and grab bars in the toilet or tub are sometimes used.
- To reach things, you might use long-handled reachers.

Basically, I am interested in whether "in the past week" you used any devices or help from another person to perform these activities.

In the **PAST WEEK**, ON AVERAGE, did you use help to....

	No Help 0	Used Equip 1	Used Human Assist 2	Used Equip & Human Assist 3	Didn't perform: Health 4	Didn't perform: Non-health 5	Don't Know 7	Refused 8

m. Walk 10 feet or across a room								
If 1 or 3 selected indicate type of equipment  1=Cane(s) 2=Walker 3=Wheelchair 4=Crutches 5=Other								
n. Walk one block on a level sidewalk								
If 1 or 3 selected indicate type of equipment  1=Cane(s) 2=Walker 3=Wheelchair 4=Crutches 5=Other								
o. Climb 5 stairs								
p. Get into car								
q. Get in and out of bed								
r. Rise from an armless chair								
s. Put on pants								
t. Put on socks, shoes on both feet								
u. Get in/out of bath or shower								
v. Wash all parts of body								
w. Get on/off the toilet								
x. Reach for an item on the ground from sitting position								

Post-Fracture Instrumental Activities of Daily Living (IADLs)

I have a few more questions about common activities of daily life.

I would like to know if you did these activities during the PAST TWO WEEKS. For each activity, I'd like you to select the statement which best describes the amount of assistance you required to do each activity.

Q1. During the TWO WEEKS how did you usually get to places out of walking distance? Did you:

	1=Travel alone on buses, taxis, or drive your own car	Go to Q2
	2=Have someone to help you or go with you when traveling	Go to Q2
	3=Did not perform: health reason	Go to Q2
	4=Did not perform: non-health reason	Go to Q1a

Q1a. If you did not travel, could you travel:

	1=Independently
	2=With Assistance

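### The SAP's rule for IADL dependence classifies a health-reason non-performer only by a follow-up question that the printed forms skip for that answer

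*SAP*

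**What the plan says.** SAP 2.10.3.2.1 first gives a general definition: "entirely dependent means that the subject is unable to perform the activities without assistance". It then illustrates this with IADL Q1, on getting to places beyond walking distance. Response 1 is not dependent and response 2 is dependent. Responses 3 and 4 are handled together through Q1a: not dependent if Q1a is 1, and dependent under "Response 3 or 4 (Did not perform), if Q1a has a response of 2 (With Assistance) or 3 (Would not be able to at all".

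The forms in Protocol Appendices 15.6 (pre-fracture) and 15.7 (post-fracture) route these two responses differently. The row "3=Did not perform: health reason" sends the interviewer to Q2. The row "4=Did not perform: non-health reason" is the only one that leads to Q1a. The interviewer instructions explain the health category as meaning that "s/he found it too difficult or unsafe to perform the activity (Did Not Perform: Health".

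The dependence rating feeds both Cochran-Mantel-Haenszel analyses and the definition of change: "A significant change from screening would be a change in the subjects entirely dependent rating". The same section also plans an item summary: "Each activity of daily living for each visit collected will be summarized using mean, standard deviation, median, minimum and maximum".

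**The concern.** The rule needs an answer that the form does not ask for. The path it leaves out is a subject who did not do the activity because it was too difficult or unsafe, which matters for a dependence endpoint in hip-fracture recovery. Both forms share the skip, so the gap can arise at screening, the reference for change, as well as at every later visit.

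The SAP does not say what happens to a response 3 with a blank Q1a. Followed literally, the subject meets neither condition and is not counted as dependent. A programmer might instead set the rating to missing. SAP 2.16 then presents last observation carried forward at Month 3 and Month 6 for efficacy endpoints with several post-baseline visits, whereas Protocol 9.6 rules out substituting missing data. Another programmer might apply the general definition and code the subject as dependent. These choices give different counts and possibly different between-arm comparisons.

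Timing matters too. Under SAP 2.11 the primary analysis shows results by actual treatment group, while PADLs and IADLs are left to the final analysis. A class chosen after that point would be chosen with group results known.

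**Working it through.** The plan gives no figure to reproduce here. The check compares the rule with the skip pattern, then illustrates size under stated assumptions.

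**Step 1: answer paths for Q1** (forms in Appendices 15.6 and 15.7; rule in SAP 2.10.3.2.1)

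| Q1 | Q1a asked on form? | Q1a | Class under the SAP rule |
|---|---|---|---|
| 1 | no | - | not dependent |
| 2 | no | - | dependent |
| 3 (health) | no | blank | none |
| 4 (non-health) | yes | 1 | not dependent |
| 4 | yes | 2 | dependent |
| 4 | yes | 3 | dependent |

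Six paths, five classified. Q2 and Q3 have the same skip, so extending the example to them gives 3 x 6 = 18 paths and 3 x 5 = 15 classified. For Q4 the form visibly sends response 4 to Q4a; the targets for responses 1 to 3 are truncated in the text.

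**Step 2: effect of the handling on the reported share.** All shares are assumed. Let d be the share otherwise dependent, h the share giving response 3, and p the proportion of response-3 subjects who really are dependent. The worked example allows p below 1, because it lets response 3 with Q1a = 1 be not dependent.

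- True share: d + p x h
- Response 3 not counted as dependent: d
- Response 3 dropped, no carry-forward: d/(1 - h)
- Response 3 counted as dependent: d + h

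With d = 30%:

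| | h = 10% | h = 20% |
|---|---|---|
| Not counted | 30.0% | 30.0% |
| Dropped | 0.30/0.90 = 33.3% | 0.30/0.80 = 37.5% |
| Counted as dependent | 40.0% | 50.0% |
| True, p = 25% | 32.5% | 35.0% |
| True, p = 50% | 35.0% | 40.0% |
| True, p = 100% | 40.0% | 50.0% |

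At h = 20%, dropping is 12.5 points low if p = 100%, 2.5 low if p = 50%, and 2.5 high if p = 25%. Dropping understates only when p exceeds d/(1 - h), here 37.5%. Counting everyone as dependent is exact at p = 100% but 10 points high at p = 50%. It is further from the truth than dropping when p is below [h + d/(1 - h) - d]/(2h) = (0.20 + 0.375 - 0.30)/0.40 = 69%. With carry-forward, none of these formulas need apply.

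**Step 3: between arms.** Assume d = 30% in both arms, h = 20% on placebo and 10% on active, the remaining 10% having become independent. The true difference is p x 10 points: 5 at p = 50%, 10 at p = 100%. The handlings show 30 - 30 = 0 (not counted), 37.5 - 33.3 = 4.2 (dropped) and 50 - 40 = 10 (counted as dependent).

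**Step 4: against sampling error.** SAP 2.14 expects about 23 completers per group. At an assumed 40% dependent, the 95% half-width of a difference is 1.96 x sqrt(2 x 0.4 x 0.6/23) = 0.283, about 28 points. The largest discrepancy in Step 3 is 10 points. An h of 5% to 30% is 23 x 0.05 = 1.2 to 23 x 0.30 = 6.9, or about 1 to 7 subjects per arm.

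**The case against.** **The Q1 text is only an example.** It follows a general definition, and a sensible programmer would class response 3 as dependent under that definition. This stands in part: nothing says that the illustration overrides the definition, and a reader who inferred that would go too far. But the example names response 3 and allows it to be not dependent, so the definition alone does not settle the coding.

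**The eCRF may collect Q1a after response 3.** It is not in the documents, so this cannot be excluded. Against it, the printed form is the interview script: "I am going to be asking you questions that are written down for me in this booklet". The fix allows for either case.

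**Classing all response-3 subjects as dependent may be worse than dropping them.** On the illustrative model that is true when p is low (Step 2). If response 3 means what the interviewer instructions say, p may be near 1, but that is not established. This objection stands and is why sensitivity analyses in both directions are needed.

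**A reader might also infer that the item mean and SD have nothing ordered behind them, or that a refusal coded 8 would be averaged in.** The documents do not support that. The section defines a two-level dependence rating that can be averaged or ranked, PADL codes 0 to 3 rise with dependence, no text plans to average refusals, SAP 2.1 provides frequency counts for categorical variables, and the table shells (SAP 4.3) are in a separate file that is not available. What remains is that the plan does not say which item value is used, which is a clarification.

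**Conclusion.** The mismatch is real and nothing elsewhere in the two documents repairs it. The stated rule cannot classify IADL Q1 response 3 on the printed forms. Taken literally, it never counts as dependent a subject who did not do the activity for health reasons, although the SAP's own definition points that way. The same gap follows for Q2 and Q3 if the example is extended.

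The size and direction of any distortion are unknown. A reader might infer that dependence is bound to be understated, or that a treatment effect would be hidden. Neither follows: the sign depends on p and on the handling, which could be non-counting, deletion or carry-forward. Every share above is assumed. In those illustrations the between-arm discrepancy is well inside sampling error.

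The endpoints are exploratory and outside the primary-analysis list in SAP 2.11, so the primary result and the sample size are unaffected. The point is worth fixing because the rule fails as written and the repair is cheap.

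**What to change.** Before any treatment-group results are seen, and so before the SAP 2.11 primary analysis:

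- Class IADL response 3 as entirely dependent under the general definition, and apply the follow-up question to response 4 only.
- State that the rule extends to Q2-Q4.
- If the eCRF did collect the follow-up after response 3, say so and use that answer instead.
- Add sensitivity analyses with response 3 treated as not dependent and as missing, stating whether last observation carried forward applies to the missing version.
- As a clarification only, name the item value behind the mean and SD, the Wilcoxon signed-rank test and the Kruskal-Wallis test (for example, the dependence rating already defined), and state that Don't Know and Refused are missing.

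The cost is minor SAP wording, derivation code and a few extra exploratory sensitivity tables. No new data are needed.
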